### *Spatial Cognition Tasks*

Spatial cognition was assessed using a variety of virtual 3D navigation tasks, which probes similar cognitive functions as real-world navigation and recruit similar neural networks (Cushman et al., 2008; Ekstrom et al., 2003; Wolbers et al., 2004). These tasks specifically target the hippocampus and other areas that support the encoding and retrieval of spatial locations, show considerable connectivity to the hippocampus, and support visuospatial imagery, episodic memory retrieval and self-processing operations. A subset of these tests has been specifically developed for in-flight assessments, which is currently prepared for flight certification in collaboration with Cadmos/ESA as part of the ISS experiment HypoCampus. This subset has been optimized relative to crew burden/compliance and scientific return, and with the respect to the underlying test constructs. Briefly, we employed a virtual cognitive map task to assess spatial memory formation (Craig et al., 2016); navigation strategies were tested using a modified paradigm originally proposed by Wiener et al. (2013), which allowed us to evaluate the selection and adoption between beacon, response cue, and spatial strategies. We also employed a plus maze task to specifically assess switching capabilities between navigational strategies (Harris et al., 2012). This paradigm has been shown to be sensitive to navigational switching, which is likely to be attributed to decreased functional connectivity between the hippocampus and pre-frontal cortex as well as dysregulation of the locus coeruleus noradrenergic system. To specifically target topographical memory, a digital version of the Four Mountains Task was performed (Chan et al., 2016; Hartley & Harlow, 2012). Path integration was assessed using a triangle completion task (Goeke et al., 2015). The task has been specifically adapted to the needs of spaceflight with respect to directions (including pitch and yaw), duration, velocity and complexity. In addition, a modified paradigm suggested by Wolbers et al. (2008) was employed to specifically assess spatial updating. Spatial orientation ability was

determined using the Perspective Taking paradigm suggested by Hegarty & Waller (2004). All tasks have been successfully established as part of various NASA/ESA and DLR studies (e.g. HERA C3, HERA C4, ESA Bed Rest 'RSL', ESA Bed Rest 'Cocktail'). The frequency of tests administrations was optimized for each task and varied between single up to daily test administrations.

### *Spaceflight Relevant Operational Tasks*

The Robotic On-Board Trainer (ROBoT) was used as an in-lab operational task. ROBoT is NASA's platform for training astronauts to perform docking and grappling maneuvers using the Canada Arm. Proficiency with this system is mandatory for all astronauts who fly. The system is based on highly realistic 3D simulations of the arm and associated physics. The physical system involves a left-hand translational controller (x/y/z directions) and a right-hand rotational controller (pitch/roll/yaw), plus two laptop computer screens. The key performance metrics include: (i) docking position accuracy, (ii) docking orientation accuracy, (iii) total task time, and (iv) smoothness of approach trajectory.

The Six Degrees of Freedom Docking Simulator (6DF) was used as an in-lab operational task. It is a high fidelity docking simulation task that has been used to investigate the performance of cosmonauts in the manual docking of a Soyuz spacecraft on the ISS. The experimental docking simulator consists of a series of docking flight tasks of varying skill level that have dynamic and informational equivalence to real docking maneuvers, based on mathematical models for real-hand control of the Soyuz spacecraft. In the evaluation of flight quality, there are 12 physical/mathematical parameters that describe the position and the motion of the spacecraft and space station with regard to each other.

The Lunar Landing Simulation was used as an in-lab operational task. It includes a sequence of activities from the Apollo Program and the Autonomous Landing and Hazard Avoidance Technology (ALHAT) Project. Subjects operate the terminal descent phase of a lunar landing. To complete the landing there is a primary flight display, landing display, and automatic and manual control modes.

## **STATISTICAL APPROACH**

We conducted a randomized, double-blind, cross-over laboratory study on the effects of the slow-wave enhancing smart sleep technology on cognitive performance during 4 consecutive nights of sleep restriction (5h time in bed). We compared the four auditory stimulation modalities (continuous fixed interval, block, in-phase adjustable, and sham) relative to their slow-wave and performance enhancing properties. Each subject was exposed to all 4 modalities (within-subject study design). We used a balanced orthogonal Latin Square design (i.e., each stimulus modality will appear in each of the 4 sleep restriction nights exactly once, and each modality will be preceded by each other modality exactly once).

Cognitive test data were standardized to baseline performance. We used linear mixed effect models (in SAS version 9.4, SAS Institute, Cary, NC) with random subject intercept to account for the clustered nature of the data. The model included factors for stimulus modality (4 levels), sleep restriction night (4 levels), and their interaction. We were both interested in the main effects (modality and sleep restriction) and their interaction, but acknowledge the limited power for detecting a significant interaction. If the type-III fixed effect estimate indicates a significant difference between groups, we compared them in post-hoc tests. The primary outcome was the number of lapses (errors of commission; response times >355 ms) on the brief Psychomotor Vigilance Test (PVT-B) after emergent awakenings and during the day. Performance on the Digit Symbol Substitution (DSST), Descending Subtraction Task (DST), and spaceflight relevant task (ROBoT) were treated as secondary outcomes. The other cognitive tests (Cognition, Spatial Cognition, tasks with operational relevance for spaceflight) were treated as tertiary outcomes. Statistical tests for secondary and tertiary outcomes were adjusted with the false discovery rate method (Curran-Everet, 2000).

For the power calculations (Figure 4), we assumed a correlation between measurements of 0.8, and varied the standard deviation of the difference between modalities/sleep restriction nights from 0.8 to 1. We expect to have >80% power to find a medium effect size of 0.5 statistically significantly different for standard deviations <0.9.

[figure not shown]

Figure 4: Power calculations

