## STUDY DESIGN

The study was conducted at the University of Pennsylvania. This placebo-controlled, double-blind, cross-over laboratory study of SmartSleep stimulations included sleep restriction to 5h time in bed for sleep on 4 consecutive nights, preceded by an 8h sleep adaptation night, and followed by a 10h recovery night (Figure 2).

The proposed sample was a total of 12 subjects to be recruited and screened for their ability to engage in the protocol and their similarities to astronauts (e.g., age 30-55y, educational background, healthy, etc.). The protocol involved monitoring of sleep-wake behaviors by actigraphy and sleep diary 2 weeks prior to and 1 week following the 7-day laboratory protocol. Participants were required to remain in the laboratory for the entire 7- day and 6-night protocol for cognitive testing at alarm awakening from sleep (sleep inertia test battery) and throughout each 19h waking period (full Cognition test battery every 4 hours). In addition, participants completed a spatial cognition battery and three tasks with operational relevance to spaceflight (Six Degrees of Freedom, ROBoT, and the Lunar Lander Simulator) once a day. The 6 laboratory nights consisted of a baseline night (8h time in bed [TIB]), 4 nights of 5h TIB (each with one of the four SmartSleep stimulus conditions), and a recovery night of 10h TIB at the end. Each of the 12 subjects received one of the SmartSleep stimulus conditions (Continuous Fixed Interval, Block,

In-Phase Adjustable, and Sham) on one of the 4 sleep restriction nights, according to a balanced orthogonal Latin Square design. This was a fully within-subjects design with high statistical power for the given sample size. This allowed us to investigate how the methodology works across the build-up of chronic sleep restriction (Figure 2).

Subjects	1	2	3	4	5	6	7	8	9	10	11	12
Lab Day 1	Familiarization testing: Cognition performance testing and operational simulation testing											
Night 1 (8h TIB)	Adaptation to SmartSleep cap: sham stim recording nocturnal sleep EEG with no emergent awakening											
Lab Day 2	Cognition performance testing and operational simulation testing											
Night 2 (5h TIB)	Sham	Stim 1	Stim 2	Stim 3	Sham	Stim 1	Stim 2	Stim 3	Sham	Stim 1	Stim 2	Stim 3
	Emergent Awakening (Sleep Inertia Test Bout)											
Lab Day 3	Cognition performance testing and operational simulation testing											

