Night 3 (5h TIB)	Stim 1	Sham	Stim 3	Stim 2	Stim 3	Stim 2	Stim 1	Sham	Stim 2	Stim 3	Sham	Stim 1
	Emergent Awakening (Sleep Inertia Test Bout)											
Lab Day 4	Cognition performance testing and operational simulation testing											
Night 4 (5h TIB)	Stim 2	Stim 3	Sham	Stim 1	Stim 1	Sham	Stim 3	Stim 2	Stim 3	Stim 2	Stim 1	Sham
	Emergent Awakening (Sleep Inertia Test Bout)											
Lab Day 5	Cognition performance testing and operational simulation testing											
Night 5 (5h TIB)	Stim 3	Stim 2	Stim 1	Sham	Stim 2	Stim 3	Sham	Stim 1	Stim 1	Sham	Stim 3	Stim 2
	Emergent Awakening (Sleep Inertia Test Bout)											
Lab Day 6	Cognition performance testing and operational simulation testing											
Night 6 (10h TIB)	Recovery sleep: sham stim recording nocturnal sleep EEG with no emergent awakening											

Figure 2: Overview of the study design. Each of the 12 subjects underwent one adaptation night (8h TIB), four sleep-restriction nights (5h TIB), and one recovery night (10h TIB). Each subject was exposed to all four SmartSleep acoustic stimulations on the four sleep restriction nights (Stim1: Continuous Fixed Interval; Stim2: Block; Stim3: In-phase adjustable; and Sham) according to a balanced orthogonal Latin Square design. Subjects performed a sleep inertia test bout consisting of a 3-min. Psychomotor Vigilance Test (PVT-B) and a Digit-Symbol Substitution Test (DSST) after emergent awakenings. They also performed cognitive and operational testing throughout the wake periods.

The following cognitive and spaceflight-relevant operational tasks were administered throughout the waking period on all days of the protocol (Figure 3):

[figure not shown]

Figure 3: Schematic of study timeline including the sampling frequency of cognitive performance and

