The Cognition battery (Basner et al., 2015; Moore et al., 2017) was administered on calibrated laptop computers. On average, 5 ISS astronauts required only 16.5 min to answer a brief survey followed by their performance on the 10 Cognition tests. We have generated software that automatically extracts key Cognition accuracy and speed outcomes. Facilitating our large database of Cognition tests, we determined loading and difficulty of individual stimuli via Item Response Theory (Embretson and Reise, 2000), which increases the power for our analyses relative to analyses based on standard accuracy outcomes (e.g., percent correct). The data analysis process was as follows: (1) extract one key accuracy and speed outcome for each test; (2) correct outcomes for practice and stimulus set difficulty effects; and (3) standardize outcomes based on baseline performance of all subjects (we will also generate speed, accuracy, and efficiency scores across cognitive domains).

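### The plan does not say whether repeated daytime tests are averaged by day; applied to test-level rows, its subject-only random intercept gives wrong error bars for modality, night and their interaction.

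*Combined protocol and SAP*

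**What the plan says.** - **Assignment.** Study Design: "Each of the 12 subjects received one of the SmartSleep stimulus conditions" on each of the four restriction nights, in the layout of Figure 2.
- **Repetition.** Testing runs "throughout each 19h waking period (full Cognition test battery every 4 hours"). The Figure 2 caption adds: "They also performed cognitive and operational testing throughout the wake periods". The Figure 3 caption also describes a separate short battery of PVT, DSST and DST. Its daily count is only in the figure, which is not shown.
- **Model.** Statistical Approach: "The model included factors for stimulus modality (4 levels), sleep restriction night (4 levels), and their interaction". Clustering is handled "with random subject intercept to account for the clustered nature of the data". The section gives no subject-by-night term, time-of-day factor or denominator-df method.
- **Primary outcome.** PVT-B lapses "after emergent awakenings and during the day".
- **Scoring.** The Cognition Test Battery section lists its steps as "1) extract one key accuracy and speed outcome for each test; (2) correct outcomes for practice and stimulus set difficulty effects"; and then "standardize outcomes based on baseline performance of all subjects (we will also generate speed, accuracy, and efficiency scores across cognitive domains"). The only combining named there is across domains, not across the bouts of a day.

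**The concern.** Stimulation is delivered once per night, so the next day's bouts are repeated readings of one experimental unit. A random subject intercept absorbs stable differences between people. It does not absorb a good or bad day for the same person. With bouts as rows, that day-to-day variation stays in the modality, night and interaction contrasts, while the residual that judges them comes mostly from differences between bouts within a day.

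A chance difference between days could then be declared a benefit of stimulation or a modality-by-night interaction. If performance varies strongly over the waking day and this is not modelled, the residual is inflated instead and a real effect could be missed. Daytime cognition is the subject of Aim 2 and of part of Aims 3 and 4.

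**Working it through.** **1. The plan's own figure.** The power paragraph claims more than 80% power for an effect of 0.5 with SD below 0.9 and correlation 0.8. I take one value per subject per condition, n = 12, a paired t-test and two-sided alpha 0.05 (assumed; none is stated), and read the SD as that of a single measurement:

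SD of difference = SD x sqrt(2 x (1 - 0.8)); noncentrality = 0.5 / (SD of difference / sqrt(12)).

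At SD 0.89 these are 0.563 and 3.08, giving 80.0% power. At SD 0.90 power is 79.1%. The claim therefore reproduces as a comparison with one value per condition.

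**2. Degrees of freedom.** Subjects take 12, modality 3, night 3 and interaction 9, so the rank is 27 (confirmed on the Figure 2 layout). One value per subject-night leaves 48 - 27 = 21 error df. With b bouts per day, another 48(b - 1) between-bout df join the residual:
- b = 4: 21 + 144 = 165, of which 87% is between-bout.
- b = 5: 21 + 192 = 213, of which 90% is between-bout.

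The 4 to 5 bouts come from 19 / 4 = 4.75 for the Cognition schedule.

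**3. Error term.** Set within-subject variance to 1, and let r be the share between subject-nights (ICC; not in the documents). With no true effect:
- expected effect mean square = 1 + (b - 1)r
- expected residual mean square = [21(1 + (b - 1)r) + 48(b - 1)(1 - r)] / [21 + 48(b - 1)]

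At b = 4, r = 0.2: 1.6 against (33.6 + 115.2)/165 = 0.902, a ratio of 1.77. At b = 5, r = 0.3: 2.2 against (46.2 + 134.4)/213 = 0.848, a ratio of 2.59. A valid test has a ratio of 1.

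**4. Type I error, test-level rows, no time-of-day effect.** Null simulation on the Figure 2 layout, complete data, 10,000 runs per cell, nominal 5%. Entries are 4 / 5 bouts.

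| ICC | Modality | Interaction |
|---|---|---|
| 0 | 5.1% / 5.0% | 5.2% / 5.2% |
| 0.05 | 8.5% / 9.3% | 10.2% / 13.2% |
| 0.1 | 12.0% / 14.7% | 18.5% / 23.5% |
| 0.2 | 21.0% / 27.3% | 37.7% / 46.6% |
| 0.3 | 30.8% / 38.5% | 54.7% / 67.2% |

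Night is within 1 point of modality. A REML fit with a random subject intercept (4,000 runs, ICC 0.1) agrees: modality 13.1% / 14.7%, interaction 18.1% / 24.1%. Because the PVT-B count is unknown, other counts were tried: over ICC 0.05 to 0.3, modality is 6% to 15% at 2 bouts and 13% to 54% at 8. Poisson lapse counts (mean 2 or 4) give modality 12% / 15% at ICC 0.11 and 23% / 28% at ICC 0.22.

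**5. Adding a time-of-day effect.** A pattern shared by all days cancels from comparisons between days, but with variance V it adds 48bV to the residual sum of squares. At b = 4, r = 0, V = 0.5 the residual becomes (165 + 96)/165 = 1.58, a ratio of 0.63. Simulated modality error, 4 / 5 bouts:

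| ICC | V = 0.25 | V = 0.5 | V = 1.0 |
|---|---|---|---|
| 0 | 1.6% / 1.7% | 0.6% / 0.8% | 0.1% / 0.1% |
| 0.1 | 5.9% / 7.2% | 2.7% / 3.7% | 0.5% / 1.1% |
| 0.2 | 12.4% / 15.4% | 6.2% / 9.7% | 1.8% / 3.2% |
| 0.3 | 19.3% / 25.7% | 11.7% / 16.7% | 4.1% / 7.4% |

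**6. Remedies.** One value per subject-night gave 4.4% to 5.5% for all three tests in all 40 Gaussian cells at 4 and 5 bouts, and 3.9% to 5.1% for counts. Bout rows with a random subject-by-night intercept and a fixed bout factor gave 2.7% to 5.4%. A bout factor alone left modality at 12% to 39% for ICC 0.1 to 0.3.

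**The case against.** The strongest reply is that this is an unstated detail. The power paragraph uses a single correlation and a single SD between modalities or nights, and its claim reproduces with one value per condition. The model has no bout or time-of-day factor, which also fits daily values. The scoring steps concern Cognition, a tertiary outcome, so their silence says little about the primary model. This stands as a hint in favour of daily values, but planning power on one value per condition does not fix the rows of the analysis.

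Three limits also stand:
- No section says that the Cognition battery contains the PVT-B. If the daytime PVT-B was given once a day, the primary outcome is untouched.
- Neither the size nor the direction of the error can be read from the documents.
- Daily means are not proof against everything. With subject-specific trends over nights (assumed slope SD 0.3 to 0.5 per night), the night test on daily means rose to 5.8% to 7.2%, while modality stayed near 5%.

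A reader might infer that bouts were entered as rows and that daytime findings are therefore false positives. The documents support neither step: the rows are undefined, there is no inflation at ICC 0, and a large time-of-day effect makes the tests conservative.

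**Conclusion.** The concern holds as an unspecified unit of analysis with a real consequence, not as a demonstrated error. The stated model is sound for one value per subject-night. On the unaveraged data that the plan describes, its only clustering term gives the wrong error term for all three daytime tests. At 4 to 5 bouts, ICC 0.1 to 0.3 and no time-of-day effect, type I error is about 12% to 39% for modality and 19% to 67% for the interaction. With time-of-day variance equal to the within-subject variance, modality falls to between 0.1% and 7.4% over ICC 0 to 0.3. Bout count, ICC and time-of-day variance are all assumptions.

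The exposed analyses are Aim 2, the cognitive parts of Aims 3 and 4, and daytime PVT-B lapses if tested more than once a day. The emergent-awakening PVT-B, Aim 5 and the once-daily tasks are not affected. The change should be made; confidence is medium, because daily values may already have been used.

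**What to change.** In the Statistical Approach section, state the unit of analysis. For each repeated daytime outcome, use one value per subject-night: the mean of the bouts on the day after that night. Alternatively, keep bout-level rows and add both a random subject-by-night intercept and a fixed bout (time-of-day) factor. With complete data and exchangeable nights, daily means hold type I error near 5%.

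State also how many daytime PVT-B bouts were given per day, so that a reader can tell whether the primary outcome is involved.

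The cost is one averaging step and a sentence or two, with no new data. Standard errors may be larger than in a naive bout-level fit. If daily values were already used, the sentence alone closes the point.

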**SmartSleep** offers an alternative to the dilemma of risking the adverse effects of chronic sleep restriction and low sleep quality in spaceflight, versus risking the adverse effects of medications on sleep and waking in ever-longer duration spaceflight. If increased amounts of slow-wave activity in sleep via SmartSleep can translate to cognitive performance benefits and/or sleep quality benefits, even during periods of chronically restricted sleep time to 5h/night, it will offer a significant advantage over the sleep medication alternative. If this is the case, it will also be essential to determine whether the enhanced slow-wave activity during sleep provided by SmartSleep will increase sleep inertia and thereby impair cognitive performance immediately following an emergent awakening. It is therefore imperative that the safety of increasing slow-wave activity be demonstrated to benefit subsequent waking cognitive performance while not exacerbating sleep-inertia performance deficits at emergent awakening. Operational safety needs to be demonstrated before the use of SmartSleep in the space program. Finally, to the best of our knowledge, a non-pharmacological slow-wave enhancing technology has not been tested in a chronic sleep restriction paradigm, despite the high prevalence of chronic sleep loss in astronauts and in the general population.

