## SPECIFIC AIMS

The overarching goal of this project is to mitigate the effects of chronic sleep loss by optimizing the SmartSleep technology and demonstrating its safety at the same time. It has the following Specific Aims:

**Specific Aim 1:** Determine whether slow-wave sleep can be enhanced via closed-loop auditory stimulation of EEG slow waves in healthy adult subjects using SmartSleep Headband technology, when sleep is restricted in duration to 5h per night over 4 consecutive nights.

Hypothesis 1: Slow wave sleep will be enhanced via closed-loop auditory stimulation of EEG slow waves relative to sham stimulation, when sleep is restricted in duration to 5h per night over 4 consecutive nights.

**Specific Aim 2:** Determine whether post-sleep cognitive performance functions sensitive to sleep restriction can be enhanced when SmartSleep closed-loop auditory stimulation is used on sleep-restricted nights relative to a sham SmartSleep control condition. Hypothesis 2: Daytime cognitive performance will be higher after closed-loop auditory stimulation of EEG slow waves relative to sham stimulation, when sleep is restricted in duration to 5h per night over 4 consecutive nights.

**Specific Aim 3:** Identify the acoustic stimulation modality with maximal benefits for slow-wave enhancement and daytime cognitive performance, when sleep is restricted in duration to 5h per night over 4 consecutive nights. Hypothesis 3: One of the three acoustic stimulation modalities enhances EEG slow waves significantly better than the other two modalities, and is also associated with enhanced cognitive performance during the daytime, when sleep is restricted in duration to 5h per night over 4 consecutive nights.

**Specific Aim 4:** Investigate systematic effects of consecutive nights of sleep restriction on slow-wave enhancement and daytime cognitive performance. Hypothesis 4: With increasing homoeostatic sleep drive induced by consecutive nights of sleep restriction, the observed slow-wave enhancement will mitigate some of the effects of chronic sleep loss on daytime cognitive performance.

**Specific Aim 5:** Assess any potential adverse effects of SmartSleep utilization during sleep restriction, especially related to sleep inertia after emergent awakening. Hypothesis 5: Cognitive functioning after emergent awakenings in the acoustic stimulation conditions will be non-inferior relative to sham stimulation based on a non-inferiority margin of 2 lapses on the PVT-B.

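### Hypothesis 5 claims non-inferiority to sham within 2 PVT-B lapses, but the planned analysis tests only for a difference and never uses the margin

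*Combined protocol and SAP*

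**What the plan says.** Specific Aim 5 concerns adverse effects, chiefly sleep inertia after an emergent awakening. Its hypothesis is that the stimulation conditions are "non-inferior relative to sham stimulation based on a non-inferiority margin of 2 lapses on the PVT-B". The margin appears nowhere else. The Background section explains why the question matters: "Operational safety needs to be demonstrated before the use of SmartSleep in the space program".

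The Statistical Approach section is the only analysis section. It specifies a linear mixed model with a random subject intercept and factors for modality, restriction night and their interaction. Four statements in it bear on this point:

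- Outcome: "The primary outcome was the number of lapses", measured "on the brief Psychomotor Vigilance Test (PVT-B) after emergent awakenings and during the day".
- Scale: "Cognitive test data were standardized to baseline performance".
- Decision rule: "If the type-III fixed effect estimate indicates a significant difference between groups, we compared them in post-hoc tests".
- Power: "We expect to have >80% power to find a medium effect size of 0.5 statistically significantly different for standard deviations <0.9".

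The section gives no non-inferiority test, confidence-interval rule, alpha or sidedness. Multiplicity adjustment is stated only for secondary and tertiary outcomes.

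**The concern.** A non-inferiority claim needs evidence that harm larger than the margin has been excluded. A test of difference asks something else: whether the four modality means are detectably unequal. A null result can mean no harm, or it can mean too little precision to see harm, and the plan has no step that separates the two.

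The gating makes this worse. Stimulation-versus-sham comparisons follow only a significant overall test, so the plan is least likely to reach the comparison Aim 5 needs when the device is in fact harmless. The documents do not say what a null result would mean for Aim 5. That leaves room for it to be read as evidence of safety, on the question the protocol itself treats as a precondition for use in spaceflight.

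**Working it through.** **1. The plan's own power figure.** Take n = 12, a paired t-test and two-sided alpha 0.05 (assumed). Read the stated SD of 0.8 to 1 as the SD of one measurement, with correlation 0.8:

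- SD of difference = SD × √(2 × (1 − 0.8)). At SD 0.9 this is 0.9 × √0.4 = 0.569.
- Noncentrality = 0.5 / 0.569 × √12 = 3.04, so power is 0.791 (11 df). At SD 0.89 it is 0.800.

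The claim of more than 80% therefore reproduces, within rounding, as power to detect a difference. (Read literally as the SD of the difference, 0.9 gives 0.420; this does not affect the present point.) Nothing in the calculation involves 2 lapses.

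**2. Residual degrees of freedom.** From the Figure 2 layout (12 subjects × 4 nights = 48 observations), subject plus modality × night has rank 27, leaving 48 − 27 = 21 df. Without the interaction the rank is 18, leaving 30 df. In both models the night-averaged stimulation-minus-sham contrast has variance 2σ²/12, where σ² = SDdiff²/2.

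**3. How often the overall test misses a true 2-lapse harm.** The noncentrality of F(3, df) is 12 × Σ(μ − mean)² / (SDdiff²/2).

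- One harmful modality, μ = (0,2,0,0): mean 0.5, sum of squares 0.25 + 2.25 + 0.25 + 0.25 = 3.
- All three harmful, μ = (0,2,2,2): mean 1.5, sum of squares 2.25 + 3 × 0.25 = 3, so the result is the same.
- Two harmful, μ = (0,2,2,0): mean 1, sum of squares 4.

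Example: at SDdiff = 3 with one harmful modality, noncentrality = 12 × 3 / 4.5 = 8, and P(non-significant) = 0.435 with 21 df.

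**4. What a non-inferiority analysis could deliver.** The standard error is SDdiff/√12 and the half-width is t(0.975, df) × SE. At SDdiff = 3 with 21 df: SE = 0.866 and half-width = 2.080 × 0.866 = 1.80. With a true difference of 0, power is the probability that a noncentral t with noncentrality 2/SE = 2.31 exceeds 2.080, which is 0.596. Power for all three modalities together comes from 1,000,000 simulated trials with a shared sham arm.

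| Assumed SDdiff (lapses) | 1.5 | 2 | 3 | 4 | 5 |
|---|---|---|---|---|---|
| F test misses harm, one or all three at +2, 21 df | 0.005 | 0.085 | 0.435 | 0.662 | 0.775 |
| Same, 30 df | 0.003 | 0.070 | 0.409 | 0.645 | 0.764 |
| F test misses harm, two at +2, 21 df | 0.0004 | 0.026 | 0.297 | 0.560 | 0.708 |
| 95% CI half-width, 21 df | 0.90 | 1.20 | 1.80 | 2.40 | 3.00 |
| Non-inferiority power, one modality, 21 df | 0.993 | 0.910 | 0.596 | 0.379 | 0.262 |
| Same, 30 df | 0.994 | 0.918 | 0.608 | 0.388 | 0.268 |
| Non-inferiority power, all three, 21 df | 0.981 | 0.807 | 0.359 | 0.163 | 0.088 |
| Same, 30 df | 0.984 | 0.820 | 0.368 | 0.167 | 0.088 |

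**5. Scale.** The margin is in raw lapses, while the plan says cognitive data were standardized to baseline and does not say whether lapse counts are exempt. In Figure 2, Night 1 is described as "sham stim recording nocturnal sleep EEG with no emergent awakening", so there is no emergent-awakening value from before restriction to standardize against.

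**The case against.** The best defence is that the protocol and SAP are one document. The Specific Aims fix the comparator, outcome, setting and margin, and the outcome is part of the primary endpoint. On this view the criterion is pre-specified and only its mechanics are missing. The rule also gates post-hoc tests; it does not say that estimates or confidence limits are withheld, and the fitted model contains them. The miss rates matter only if someone reads a null test as non-inferiority, which the plan never says it will do.

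Part of this stands. The margin is pre-specified, the model can supply what is needed, and the 95% figure refers to the planned post-hoc comparison not being triggered, not to an estimate being unobtainable. The miss rates show the cost of a misreading; they are not the defect itself. But the procedure actually written is a different one, and the implied one lacks its level, sidedness, scale and handling of three comparisons.

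Standardizing with one common mean and SD would be a linear change, and the margin could be rescaled by that SD. The plan does not give the constant, so raw counts are the simpler route.

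Figure 4 was not available for this review, but the text introduces it only as power for a difference.

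**Conclusion.** The concern holds, and it must be fixed. The decision rule does not fit the hypothesis: followed as written, it cannot establish Hypothesis 5 at any SD. The consequence of misreading a null result runs from negligible (0.5% missed at SDdiff 1.5) to large (77% at SDdiff 5), and the documents give no SD in lapses to narrow that range. The calculations assume n = 12 with complete data, two-sided alpha 0.05 (one-sided 0.025 for non-inferiority), equal correlations and approximately normal errors. The last is a real approximation for lapse counts at this sample size. The finding itself rests on the text and does not depend on these assumptions.

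**What to change.** For Aim 5, write the following into the Statistical Approach section:

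- Analyse PVT-B lapses from the emergent-awakening bout as raw counts, so that the 2-lapse margin applies directly.
- From the planned model, report the two-sided 95% confidence interval for each stimulation-minus-sham difference, averaged over the four nights, whatever the type-III result. Night-averaging must be stated: under the interaction model a single-night contrast has variance 0.917σ² against 0.167σ², an interval √(0.917/0.167) ≈ 2.3 times as wide.
- Declare a modality non-inferior only if its upper limit is below +2 lapses. Claim non-inferiority for the stimulation conditions as a whole only if all three pass; that joint claim needs no multiplicity adjustment.
- Say how separate per-modality claims are handled. Unadjusted, if all three modalities are truly at +2, at least one is wrongly declared non-inferior about 6.1% of the time (simulation, shared sham, 21 df).
- State that a non-significant type-III test is not support for Hypothesis 5.

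The section is largely in the past tense, and the documents do not settle whether data had been seen. If they had, label the rule as a later clarification; the margin itself was already specified.

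The cost is wording and three intervals, with no new data. The drawback is that the trial may be unable to show non-inferiority: with no true difference, power for all three modalities is 81% at SDdiff 2 but 36% at 3 and 9% at 5 (21 df).
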